#### **Additional Information - MIRROR/USU:**

This research study is being conducted as part of Musculoskeletal Injury Rehabilitation Research for Operational Readiness (MIRROR), which is based out of the Department of Physical Medicine & Rehabilitation (PM&R) at the Uniformed Services University (USU).

MIRROR is focused on advancing musculoskeletal injury (MSI) rehabilitative care within the military healthcare system in order to reduce the burden MSIs have on military readiness and to ultimately enhance the operational capabilities of the armed forces. MSIs affect approximately 800,000 service members annually and result in 25 million days of limited duty. These conditions are the primary reasons for medical discharge/downgrade and result in 34% of medical evacuations from theatre. MIRROR was developed as a means to study risk factors of common MSIs, generate prevention strategies, optimize treatments, and establish return-to-duty criteria that is based on scientific evidence rather than case-specific clinical judgment alone.

MIRROR involves interdisciplinary and inter-service partnerships, the DoD, and several major academic medical centers. To ensure military mission focus and scientific relevance, MIRROR is guided by a steering committee composed of members from the Joint Program Committees (JPCs) at the U.S. Army Medical Research and Development Command (USAMRDC), military operational leaders, and experts in musculoskeletal medicine from the military and civilian communities. MIRROR aims to be the world's leader in military relevant musculoskeletal injury care research.

Currently, 40+ research projects are being deployed at more than 20 military and civilian treatment facilities nationwide.

MIRROR/USU is serving as a Coordinating Center for this study and will also be providing remote regulatory support. Staff from MIRROR/USU will not interact with human subjects and will not have access to the Master List during the conduct of this study. Deidentified research data will be shared with MIRROR/USU and maintained indefinitely for possible use in future research.

#### **10.2 Data Collection:**

Describe all the data variables, information to be collected, the source of the data, and how the data will be operationally measured.

Please see Appendix K Data Collection Schedule.

The local study team will obtain the information necessary to complete the study CRFs directly from the participant.

#### **Outcome Measures & Functional Assessments:**

- Defense and Veteran's Pain Rating Scale (DVPRS) basic - captures pain
- Visual Analogue Scale (VAS) - measures delayed onset muscle soreness
- Borg Perceived Exertion and Elloumi scale for behavioral health
- Quick Physical Activity Rating (QPAR) scale

- Activity log to record activity and a training log that records the THOR3 training workout for all associated participants.
- Percent body fat, height, and weight
- CMJ measurements to assess performance (deceleration/concentric impulse, peak force production, rate of force production, any asymmetries) via jump plates
- Isokinetic dynamometer to measure isolated strength.
- Oura Ring will continuously measure sleep, heart rate, Sp02, and activity.

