#### **Demographics, & Baseline Data Collection:**

Prior to receiving study treatment, participants will complete a Demographics CRF (Appendix C) which collects relevant demographics including: personal demography, military and employment demography, and study-specific demography.

Additionally, participants will complete a Baseline Data Collection CRF (Appendix D) that collects: relevant medical history, military & work status, validated self-report measures, and study-specific measures. The following study-specific measures will be collected by a study team member:

- Fitzpatrick Skin Phototype
- Height, weight, and body fat composition (measured by bioelectrical impedance with InBody 770)
- Measurements of the participant's quadriceps to calculate the appropriate PBMT dose. (See Appendix S for PBM dosing information).
- Assessments of both legs:
  - CMJ, assessing jump height, time to take-off, RSImod, Eccentric Deceleration Impulse, Countermovement Depth, Concentric Impulse, Movement Start to Peak Power, and any asymmetries, and
  - Isometric and isokinetic dynamometer testing, assessing isolated strength in the lower body (i.e., unilateral Peak Torque and Rate of Force Development of quadriceps and hamstrings).
  - Processes for these tests can be found in the Appendices L and W. CMJ data will be output from the Force Decks software and recorded directly by the study team to the Appendix D and E CRF tables at each test iteration.

Each participant will be assigned an Oura Ring at baseline. Participants will be instructed to wear the Oura Ring for the duration of the study. The Oura Ring will continuously measure sleep quality, heart rate, blood oxygen saturation percentage (SpO2) levels, and activity. Oura Ring data will be securely stored in OuraTeams with access only for research team members.

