## 11.0 Statistical/Data Analysis Plan

### 11.1 Statistical Considerations:

List the statistical methods to be used to address the primary and secondary objectives, specific aims, and/or research hypotheses. Explain how missing data and outliers will be handled in the analysis. The analysis plan should be consistent with the study objectives. Include any subgroup analyses (e.g., gender or age group). Specify statistical methods and variables for each analysis. Describe how confounding variables will be controlled in the data analysis

Descriptive statistics will report location and scale in terms of mean and standard deviation for normally distributed variables, median and interquartile intervals for ordinal metric variables, and in terms of proportion and size for categorical variables. Descriptive statistics will be reported for baseline demographic and clinical characteristics at an overall level and by initial treatment group.

Outliers will be removed if determined to be erroneous based on relevant clinical expertise. Confounding will be principally controlled by randomization. In regards to the treatment of missing data, Oura Ring data will be analyzed despite presence of missing data at any point; with regards to non-continuous outcomes, data will be analyzed only if baseline and the 3-week follow-up are both present. In the event of missing data for a mid-point follow up (i.e., not baseline or the 3-week follow up), said patient will still be included in all models.

Statistical analyses will use generalized additive models predicting the change in outcome measures at 3 weeks relative to baseline for all measures except Oura Ring data. Oura Ring data will be aggregated by averaging readings across each 24-hour period and will be modeled using multi-level models incorporating random effects. Sensitivity analyses will be performed on longitudinal data for each outcome metric and will include multi-level models incorporating random effects as well as control variables to account for any differences explained by a selection of patient characteristics (such as body weight, etc.).

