### 11.6 Data Analysis Plan: Complete description: Background, Objectives, Design, Step by Step how the project is going to be done, Data analysis plan:

Descriptive statistics will report location and scale in terms of mean and standard deviation for normally distributed variables, median and interquartile intervals for ordinal metric variables, and in terms of proportion and size for categorical variables. Descriptive statistics will be reported for baseline demographic and clinical characteristics at an overall level and by initial treatment group.

Statistical analyses will use generalized additive models predicting the change in outcome measures at 3 weeks relative to baseline for all measures except Oura Ring data. Oura Ring data will be aggregated by averaging readings across each 24-hour period and will be modeled using multi-level models incorporating random effects. Sensitivity analyses will be performed on longitudinal data for each outcome metric and will include multi-level models incorporating random effects as well as control variables to account for patient characteristics. Exact selection of control variables will be guided by observed differences within final collected data as well as relevant clinical expertise.

Hypothesis tests will be two-tailed and statistical significance will be considered at the putative threshold ( $\alpha=0.05$ ). Any secondary P-values will be subject to a false discovery rate adjustment in keeping with best statistical practices. Multilevel models will incorporate random effects to account for repeated measures, using distribution families and link functions appropriate for the outcomes of interest, determined using quantile-quantile (QQ) plots analyzed for best model fit. All statistical analyses will be performed using the R Programming language.

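### Jump asymmetry is listed as an outcome without a stated scale: if it is a signed left/right index centred near zero, the planned change score has power close to alpha, and on either scale a baseline-adjusted absolute value does better

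*Combined protocol and SAP*

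**What the plan says.** Section 10.1 (Demographics, & Baseline Data Collection) has both legs assessed by countermovement jump. Its list of jump variables ends with "Countermovement Depth, Concentric Impulse, Movement Start to Peak Power, and any asymmetries". Section 10.2 (Outcome Measures & Functional Assessments) repeats the item: "CMJ measurements to assess performance (deceleration/concentric impulse, peak force production, rate of force production, any asymmetries) via jump plates".

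On how values reach the case report form, Section 10.1 says "CMJ data will be output from the Force Decks software and recorded directly by the study team". It describes no transformation on the way. For the test procedures it says "Processes for these tests can be found in the Appendices L and W"; those appendices, and the form tables in Appendices D and E, are not in the supplied text.

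Section 11.1 sets the main analysis: "generalized additive models predicting the change in outcome measures at 3 weeks relative to baseline for all measures except Oura Ring data". Section 11.6 repeats it and adds: "Sensitivity analyses will be performed on longitudinal data for each outcome metric". These are multi-level models with random effects and control variables. Neither section makes an exception for asymmetry, rescales it, or specifies the baseline value as a model term.

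No supplied section gives a formula, a sign convention, a reference limb or a direction of benefit for asymmetry. The list of force-plate measurements in Section 17.1 does not mention it.

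**The concern.** Most outcomes here have a better and a worse direction. Asymmetry does not: its natural best value is zero, with departures possible on both sides. Suppose the index carries a sign. A right-dominant man who goes from +10 to +5 has a change of -5. A left-dominant man who goes from -10 to -5 has a change of +5. Both halved their asymmetry, and their mean change is 0.

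The plan does not say which scale applies, and the rule in 11.1 behaves very differently on the two. On a signed scale the trial could report no effect of photobiomodulation on asymmetry when there was one. If the scale is left open until outcomes have been seen by arm, the choice between signed and absolute becomes data-dependent.

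**Working it through.** **The plan's own figure.** Section 11.5 claims 80% power with 85 analysed and 90% with 108, for an effect size of .15 at the 5% level, using the linear multiple regression module of G*Power. I read .15 as f². The noncentrality is λ = f²·N: 0.15 × 85 = 12.75 and 0.15 × 108 = 16.2. The number of predictors is not stated. With four in the omnibus F test, power is 80.3% and 90.1%, so the figures reproduce. The calculation is generic and not tied to asymmetry.

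**Inputs from the documents.** Two-sided α = 0.05 (11.6); 85 analysed, 42-43 per arm (11.2); analysis variable = 3-week change (11.1, 11.6).

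**Assumptions not in the documents.** True signed asymmetry A has group mean μ and SD 8 points. Each visit adds independent error with SD 3 (reliability 64/(64 + 9) = 0.88). In the active arm the true value at week 3 is (1 − s)A, with s = 0.3 or 0.5; in the sham arm it stays A. Benefit means movement toward zero.

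**Algebra for the signed change.** The change is −sA + e₁ − e₀ in the active arm and e₁ − e₀ in the sham arm, so:

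- expected arm difference = −s·μ
- variance = s²·64 + 2·9 (active) and 2·9 = 18 (sham)

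At μ = 0 the expected difference is 0 whatever s and the SDs are, so the test rejects at about its nominal 5%. At μ = 4 and s = 0.5 the difference is −2.0. The active variance is 0.25 × 64 + 18 = 34, and the standard error with 43 and 42 men is √(34/43 + 18/42) = 1.10. The ratio is 1.81, and approximate power is Φ(1.81 − 1.96) = 44%.

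**Simulation** (3,000 runs per cell, 43 against 42). The last column compares the absolute week-3 value by arm, adjusted for the absolute baseline value.

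| μ | Reduction s | Signed change | Absolute change | Absolute, baseline-adjusted |
|---|---|---|---|---|
| 0 | 30% | 5% | 53% | 66% |
| 0 | 50% | 5% | 90% | 98% |
| 2 | 30% | 10% | 55% | 68% |
| 2 | 50% | 16% | 90% | 98% |
| 4 | 30% | 22% | 65% | 77% |
| 4 | 50% | 45% | 95% | 99% |
| 8 | 30% | 67% | 85% | 92% |
| 8 | 50% | 94% | 99% | 100% |

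The simulated 45% at μ = 4, s = 0.5 agrees with the 44% worked by hand. With no treatment effect, every analysis rejected between 4.4% and 5.5% of the time. Adjusting the signed week-3 value linearly for the signed baseline does not help at μ = 0: it rejects 5% of the time at either reduction.

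**Noisier measurement.** With a total SD of 8 and reliability from 0.70 to 0.85, at μ = 0:

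| Reduction s | Signed change | Absolute change | Absolute, baseline-adjusted |
|---|---|---|---|
| 30% | 5-6% | 20-45% | 27-58% |
| 50% | 5-6% | 42-82% | 63-96% |

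Over the same reliabilities and both reductions, the signed change reaches 13-42% at μ = 4 and 40-94% at μ = 8.

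**The sensitivity analyses.** The longitudinal models would share the cancellation if they used the same signed values. A smooth of baseline that differs by arm could pick up shrinkage toward zero, but the plan specifies no such term.

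**The case against.** The strongest reply is that the premise is not established. No supplied text says that the index is signed. Appendices D, E, L and W may settle the recording format, and if a magnitude is recorded nothing cancels. This stands, and it is why the point is conditional. It does not close the gap, because the analysis rule is in Section 11, which is silent.

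Second, asymmetry is thin as a tested endpoint. It is a closing item in two lists and absent from the list in 17.1. The outcome list in 10.2 also holds height and a training log, which nobody would test for a treatment effect, so the rule for all measures may not be meant literally. The aims in 9.3 are descriptive, and the background in 9.2 does not claim that treatment reduces asymmetry. These points limit the weight of the finding. They do not tell an analyst what to do with the variable.

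Third, the signed test still holds its type I error, so the risk is lost sensitivity and not a false positive. That is correct.

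Fourth, the gain from baseline adjustment is not special to asymmetry; it is the usual comparison of a change score with a baseline-adjusted one. Also correct: it supports the form of the fix and does not make the defect larger.

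Finally, Section 11.5 already calls the study a feasibility or pilot study that may lack power. That argues against treating this as a major fault, but not against a definition that costs one sentence.

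**Conclusion.** An outcome with no stated scale or direction falls, read literally, under a change-from-baseline rule that works poorly on one of its two natural scales. There are three cases:

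- **Signed, group mean near zero:** power is close to alpha, about 5%, whatever the size of the effect. This result does not depend on the assumed SDs.
- **Signed, group leaning to one side:** power is reduced but not lost. It ran from 10% to 94% for means of 2 to 8 points, below the absolute index in every cell of the main table.
- **Magnitude:** no cancellation. The plain change score was less sensitive than the baseline-adjusted analysis, for example 53% against 66% for a 30% reduction at a mean of 0.

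All power figures away from the zero-mean case rest on assumed SDs, reliabilities and reductions, and benefit as movement toward zero is inferred.

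A reader might infer that the planned test has no power. The documents do not support that: it needs both a signed index and a group mean near zero, and they state neither. A reader might also take the rule to cover every measure without exception, but Oura Ring data are modelled separately. Nor is there a demonstrated harm to the other outcomes through the false discovery rate adjustment in 11.6; one more uninformative P-value may enter that family, but no effect on any other result has been shown. The plan names no primary outcome, this is one of many measures, and the sample size is unaffected. It is a definitional gap worth closing because closing it is nearly free.

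**What to change.** In Sections 11.1 and 11.6, add a statement that each asymmetry outcome is analysed as an absolute left-right difference. Name the jump variables on which it is calculated. Give the formula, make it consistent with the case report form and the test appendices, and fix it before any outcome is seen by arm. State that a smaller value is the favourable direction, if that is what the investigators intend. Compare the absolute week-3 value between arms, adjusted for the absolute baseline value, and use the same absolute scale in the longitudinal sensitivity models. Report the signed index descriptively only; it will still show any man who switches side.

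If the appendices already record a magnitude, a cross-reference and the baseline adjustment are enough. If asymmetry is not meant to be tested, say that it is descriptive.

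The cost is a sentence or two in the analysis plan and one derived variable per asymmetry measure. No new data or visits are needed, and the sample size does not change.

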#### **Appendix A Inclusion Exclusion CRF:**

Verifies that the potential participant meets eligibility criteria for study participation.

- Inclusions/exclusion criteria
- Documentation of informed consent
- Final eligibility status
- Randomization documentation

#### **Appendix B Intake CRF:**

Obtains sufficient contact information in order to locate and track the participant during study participation.

#### **Appendix C Demographics CRF:**

Characterizes the participant's demographics and relevant medical and work history. This information may have a significant effect on functional outcomes.

- Personal demography
- Military & employment demography
- Study-specific demography

#### **Appendix D Baseline Data Collection CRF:**

Collects relevant baseline research data.

- Self-reported medical history
- Current military & work status
- DVPRS
- QPAR
- VAS
- Borg Perceived Exertion Scale
- Elloumi fatigue scale
- Fitzpatrick Phototyping Scale
- Body measurements
- CMJ
- Isometric/Isokinetic Strength

#### **Appendix E Follow-Up Data Collection CRF:**

Collects relevant follow-up research data.

- VAS
- Borg Perceived Exertion Scale (3-week follow-up only)
- Elloumi fatigue scale (only at 3-week follow-up)
- CMJ
- Isometric/Isokinetic Strength (3-week follow-up only)
- Adverse Event (AE) assessment

#### **Appendix F Activity Log**

- Daily activity
- Daily DVPRS

#### **Appendix G THOR3 Training Program Log CRF:**

Documents THOR3 training completed (reps, sets, load) for each study visit.

#### **Appendix H Protocol Adherence CRF:**

Documents protocol adherence for each study visit.

- AE assessment
- PD assessment

#### **Appendix J Study Completion CRF:**

Documents participant study completion status.

- Study completion status
- AE assessment
- PD assessment

#### **10.3 At any point in the study, will you request, use, or access health information in any form, including verbal, hard copy and electronic?**

Yes  No

#### **10.14 Managing Data (Data Management and/or Sharing Plan) and/or Human Biological Specimens for this Study:**

Include in this section the plan for acquiring data (both electronic and hard copy), access during the study, data/specimen storage and length of time stored, shipment/transmission, and the plan for storage and final disposition at the conclusion of the study. Describe any data agreements in place for accessing data within and/or outside of your institution (e.g., Data Sharing Agreement, Data Use Agreement, Business Agreements, etc.)

##### **Data Capture Methods:**

The local study team will collect data directly from the study participant (including in person, mail, email, or over the phone) and record it on study CRFs. The completed CRFs will serve as source documents for this study.

Participants may enter their coded data directly into REDCap using a personalized survey link (no log-in required). In these cases, the completed REDCap forms will be printed and added to the participant's research record to serve as a source document.

##### **Electronic Data Entry:**

The study team will enter non-personally identifiable data from the paper CRFs into REDCap. Please see Appendix U for additional information on REDCap.

##### **Data Storage & Access:**

The ICF and Intake CRF will be stored separately from the coded paper research forms. All paper research forms and source documents will be stored in a locked cabinet inside of a locked room within the THOR3 area.

The coded electronic research data for this study will be stored in REDCap, housed on a Department of Defense (DoD) server and maintained by USU IT. No PII will be entered into REDCap. The local study team will maintain the electronic master list separately from the coded electronic research data in a secure, password protected document on a computer and network that requires CAC access and will only be accessible by local research staff.

Access to the electronic coded research data will be governed strictly on an individual-by-individual basis within REDCap. Individual data access as well as privileges will be clearly delegated, audited, and monitored by MIRROR/USU. Staff from MIRROR/USU will not have access to the paper research records or any identifiable research data.

All research data and forms (both paper and electronic) will only be accessible by authorized study staff, authorized staff from MIRROR/USU (coded data entered into REDCap only, as described above), the IRB of record, the USASOC HRPP, and applicable governmental agencies as part of their duties and in accordance with federal law.

There will be appropriate data sharing agreements in place.

At study closure, study documents will be securely transported to USU Department of PM&R and Military Emergency Medicine (MEM) for record retention. ICFs will be maintained for a period of 6

years following study closure and then securely shredded. Paper research forms will be maintained for a period of 5 years following study closure and then securely shredded. The master list connecting unique study ID to participant identifiers will be destroyed at study closure. The electronic coded research data will be maintained indefinitely as described below in Protocol Section 10.15.

Is this a data repository?

Yes  No

## **10.15 Managing Data (Data Management and/or Sharing Plan) and/or Human Biological Specimens for Future Research:**

If the study involves collecting, storing, or banking human specimens, data, or documents (either by the Investigator or through an established repository) for FUTURE research, address. How the specimens/data will be used, where and how data/specimens will be stored (including shipping procedures, storage plan, etc.), whether and how consent will be obtained, procedures that will fulfill subjects' request as stated in the consent, whether subjects may withdraw their data/specimens from storage, whether and how subjects may be recontacted for future research and given the option to decline, whether there will be genetic testing on the specimens, who will have access to the data/specimens, and the linkage, the length of time that data/specimens will be stored and conditions under which data/specimens will be destroyed.

